Twelve-Month Short-Term Marginal Bone Remodeling at Monolithic Zirconia Full-Arch Prostheses in the Maxilla and Mandible: A Clinical Study

NCT Number:
NCT: *Not yet assigned*

Document Type:
Study Protocol

Document Date: July 9, 2020

Version:
1.0

Sponsor:
Universitat Internacional de Catalunya (UIC)

Principal Investigator: [name]

Study Sites:
Universitat Internacional de Catalunya

STUDY PROTOCOL

1. Background and Rationale

Monolithic zirconia full-arch implant-supported prostheses have gained widespread clinical use due to their high mechanical strength, esthetic longevity, and lower chipping risk compared to veneered restorations. Despite increasing adoption, limited evidence exists regarding whether marginal bone remodeling differs between maxillary and mandibular zirconia rehabilitations and whether mandibular morphology or arch geometry influence early remodeling outcomes.

Mandibular deformation during function (“mandibular flexure”) and anatomical variations such as U-shaped vs V-shaped mandibular arches may contribute to differences in bone response. This study evaluates early remodeling patterns under strictly standardized surgical and prosthetic conditions to determine whether mandibular anatomy plays a measurable role.

2. Study Objectives

Primary Objective

To compare 12-month marginal bone remodeling (MBL) between maxillary and mandibular full-arch monolithic zirconia implant-supported prostheses.

Secondary Objectives

- To evaluate whether mandibular morphology (U-shaped vs V-shaped) affects early marginal bone remodeling.
- To assess associations between arch geometry (inter-implant distance, cantilever length) and MBL.
- To evaluate 12-month implant and prosthetic survival rates.
- To assess patient-reported outcomes (OHIP-14 and VAS satisfaction).
- To document biological and mechanical complications.

3. Study Design

This is a prospective observational cohort study with a 12-month follow-up period.

All patients receive standard-of-care implant placement and monolithic zirconia full-arch prosthetic rehabilitation. No experimental intervention is assigned.

Study Groups

- **Group 1:** Maxillary full-arch rehabilitations
- **Group 2:** Mandibular full-arch rehabilitations
 - Sub-analysis: U-shaped vs V-shaped mandibles

Observation Period

Baseline (prosthesis delivery) → 12 months.

Sample Size

49 rehabilitated arches in 40 edentulous patients.

Power >85% to detect a 0.2 mm difference in MBL (SD 0.30 mm).

4. Study Population

Inclusion Criteria

- Age \geq 50 years
- Edentulous maxilla and/or mandible
- Adequate bone volume for 6–8 implant placement
- Non-smokers or light smokers (<10 cigarettes/day)
- Able to provide informed consent

Exclusion Criteria

- Bruxism
- Bisphosphonate therapy
- Uncontrolled systemic diseases
- Contraindications to implant surgery
- Active oral infection or poor hygiene

5. Surgical and Prosthetic Procedures

- Guided placement of 6–8 NobelParallel TiUltra implants per arch.
- Immediate loading with a PMMA provisional prosthesis within 48 hours.
- Delivery of the definitive monolithic zirconia prosthesis at 3 months using a full digital workflow.
- Standardized radiographs and follow-up examinations.

6. Assessments

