6.5 Patient-Reported Outcomes

- OHIP-14
- VAS satisfaction (0–10)

7. Outcome Measures

Primary Outcome

Marginal Bone Loss (mm)

Change in peri-implant marginal bone level measured from baseline to 12 months.
Higher values = greater bone loss (worse outcome).

Secondary Outcomes

1. Implant and Prosthetic Survival Rate

Percentage surviving without removal or failure. Higher % = better outcome.

2. Patient-Reported Outcomes

- OHIP-14 (0–56; higher = worse)
- VAS satisfaction (0–10; higher = better)

3. Mechanical and Biological Complications

Presence/absence and type of event.

8. Statistical Analysis Plan

- Normality: Shapiro–Wilk test
- Between-group comparisons: Two-way ANOVA
- Morphology subgroups: One-way ANOVA with Bonferroni
- Paired comparisons (bimaxillary patients): Paired t-test
- Correlations: Pearson (separately for each arch)
- Significance level: $\alpha = 0.05$

Secondary analyses are exploratory.

9. Ethical Considerations

- Approved by UIC Ethics Committee (REST-ECL-2020-02).
- Conducted in accordance with the Declaration of Helsinki.
- All participants provided informed consent.
- Data stored securely and pseudo-anonymized.

10. Data Management

- Coded, de-identified datasets stored on secure servers.
- Access limited to authorized researchers.
- Data retained for 15 years.

11. Study Timeline

- Start Date: December 2024

- Primary Completion Date: December 2025
- Study Completion Date: December 2025

12. Dissemination Plan

Results will be submitted for peer-reviewed publication and presented at scientific conferences. No identifying participant information will be released.

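### The claimed power above 85% does not follow from the protocol's own inputs: 49 arches with SD 0.30 mm give about 63% for a 0.2 mm difference

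*Protocol*

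**What the plan says.** The primary objective in Section 2 is "To compare 12-month marginal bone remodeling (MBL) between maxillary and mandibular full-arch monolithic zirconia implant-supported prostheses". Section 3 defines two groups, maxillary and mandibular rehabilitations, and gives the size as "49 rehabilitated arches in 40 edentulous patients". Directly below comes the only justification for that size: "Power >85% to detect a 0.2 mm difference in MBL (SD 0.30 mm").

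Section 8 sets the significance level at 0.05 without naming one or two sides. The relevant tests are "Between-group comparisons: Two-way ANOVA" and "Paired comparisons (bimaxillary patients): Paired t-test". Section 5 has "Guided placement of 6–8 NobelParallel TiUltra implants per arch".

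The protocol does not state how the 49 arches divide between jaws, whether the SD is per arch or per implant, or any within-patient or within-arch correlation.

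**The concern.** The difference, SD, total size and significance level are all printed, so the power can be recomputed. A difference of two thirds of an SD with roughly 25 arches per group does not look like an 85% design.

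The power line is the sole support for the study size and it concerns the primary outcome. If it is too high, a non-significant maxilla-versus-mandible result will carry more weight than it deserves. Readers would take it that a 0.2 mm difference had been looked for with less than a 15% chance of being missed.

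**Working it through.** **Inputs**
- Difference: 0.2 mm (Section 3).
- SD: 0.30 mm (Section 3), taken first as the SD between arches, because size and groups are given in arches.
- Total: 49 arches in 40 patients (Section 3). If no patient has more than two arches, 49 − 40 = 9 patients are bimaxillary and 31 contribute one arch.
- Significance level: 0.05 (Section 8). Two-sided is assumed; one-sided is also tried.
- Split between jaws: not stated. 24/25 is assumed because it maximises power.

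**1. Attempt to reproduce the stated figure**

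Standard error of the difference = SD × √(1/n₁ + 1/n₂) = 0.30 × √(1/24 + 1/25) = 0.0857 mm.

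Noncentrality = 0.2 / 0.0857 = 2.333.

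Normal approximation: power = Φ(2.333 − 1.960) = Φ(0.373) = 64.5%.

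Noncentral t with 47 degrees of freedom: 62.7%. A two-way ANOVA with 45 error degrees of freedom also gives 62.7%, so the choice between ANOVA and t-test does not matter.

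**2. Other splits and sidedness (noncentral t)**

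| Split | Sides | Power |
|---|---|---|
| 24/25 | two | 62.7% |
| 28/21 | two | 61.9% |
| 30/19 | two | 60.5% |
| 35/14 | two | 54.2% |
| 24/25 | one | 74.4% |

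No split reaches 85%, even one-sided. The paired t-test on 9 pairs, with 0.30 mm taken as the SD of the within-patient difference, gives 42.1%.

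**3. What 85% would require**

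Normal approximation, per group: n = 2 × (1.960 + 1.036)² × (0.30/0.2)² = 2 × 8.98 × 2.25 = 40.4, so 41. With the t distribution, 42 per group (85.5%), or 84 arches in total.

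Holding 24/25 fixed, 85% is reached at a difference of 0.262 mm (SD 0.30 mm) or at an SD of 0.229 mm (difference 0.2 mm).

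**4. Readings that would give more than 85%**

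- *49 arches in each group:* 90.4%. The total may have been entered as the per-group size, but this is only a possible origin.
- *SD 0.30 mm per implant, m implants per arch, analysed as arch means:* arch-mean SD = 0.30 × √((1 + (m − 1) × ICC)/m). For m = 6 and ICC 0.5 this is 0.30 × √(3.5/6) = 0.229 mm, with power 84.9%. For m = 8 and ICC 0.5 it is 0.225 mm, with power 86.1%. Setting the arch-mean SD to 0.229 mm gives a limiting ICC of about 0.50 (m = 6) to 0.52 (m = 8).
- *One combined model for 9 pairs and 31 single arches:* generalised least squares, split 24/25, noncentral t with 38 degrees of freedom (40 − 2). Power is about 62% at within-patient correlation 0, 76% at 0.5 and 85% at about 0.67.

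**5. Expected precision**

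95% confidence interval half-width = 2.012 × 0.0857 = 0.17 mm.

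**The case against.** The strongest reply is that the SD carries no unit of analysis. Section 7 defines the outcome as a change in bone level around the implant, and Section 5 puts 6–8 implants in each arch. If 0.30 mm is a per-implant SD, arch means vary less and power exceeds 85% over roughly the lower half of the ICC range (94.3% at ICC 0.3 with six implants). Pairing in the bimaxillary patients also adds information. Further, 24/25 appears nowhere in the protocol, and the protocol announces no equivalence claim.

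Part of this stands. The 63% depends on an arch-level SD, a near-equal split and independent arches, and a wrong reading of a null result is a risk rather than something the protocol proposes.

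The rest does not rescue the line. The size and the groups are expressed in arches, and no within-arch correlation is given; the ICC of 0.94 in Section 6.1 is examiner agreement, not clustering of implants. The pairing route needs a correlation of about 0.67 and a model that combines paired and single arches, whereas Section 8 lists an ANOVA and a separate paired t-test. The 24/25 split is the most favourable choice, so replacing it with the true split can only lower the figure. A separate analysis plan might supply further detail, but the protocol itself prints a power that its own inputs do not yield.

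**Conclusion.** The concern holds. On the printed inputs, power for a 0.2 mm difference is about 63% at best, more than 20 points below the claim, and the type II error is about 37% rather than under 15%. Neither sidedness, nor group split, nor choice between t-test and ANOVA explains the gap. This rests on SD 0.30 mm being between arches and on arches being treated as independent. The exact figure would change under a per-implant SD or a combined paired model, but the protocol states neither. With an expected half-width of 0.17 mm, many non-significant results would still be compatible with a true difference of 0.2 mm.

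**What to change.** Restate the power line in Section 3, for example:

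> With 49 arches (about 24/25 between jaws), an arch-level SD of 0.30 mm and two-sided alpha 0.05, power is about 63% for a 0.2 mm difference and 85% for a 0.26 mm difference.

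The sponsor should enter the actual split if it is known and recompute. If 0.30 mm was a per-implant SD, the line should say so and give the within-arch ICC used. If pairing was counted on, it should give the within-patient correlation and name the model that uses it.

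Report the maxilla-minus-mandible difference with its 95% confidence interval, and say that a non-significant result will not be read as equivalence.

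The cost is one sentence in Section 3 and a less favourable power figure. No patients are added and no clinical procedure changes.

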6.1 Radiographic Assessment

- Standardized periapical radiographs using paralleling technique and fixed exposure settings.
- Image calibration based on implant thread pitch.
- Two calibrated examiners (ICC=0.94) measure MBL; discrepancies >0.1 mm resolved by consensus.

6.2 Mandibular Morphology Classification

- CBCT-based classification using validated criteria (intercanine/intermolar ratio and anterior arch angle).
- U-shaped vs V-shaped categorization.

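### Can edentulous mandibles be classed as U- or V-shaped by an intercanine/intermolar ratio when section 6.2 names no landmarks, cut-points or combining rule?

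*Protocol*

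**What the plan says.** Section 6.2 of the protocol is the only place that describes how a mandible gets its shape class. It gives the method as "CBCT-based classification using validated criteria (intercanine/intermolar ratio and anterior arch angle") and the output as a "U-shaped vs V-shaped categorization". There is no third or unclassifiable category.

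Other places bear on it:

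- Section 4 requires "Edentulous maxilla and/or mandible", and the sample size in section 3 is "49 rehabilitated arches in 40 edentulous patients".
- Section 2 lists as its first secondary objective "To evaluate whether mandibular morphology (U-shaped vs V-shaped) affects early marginal bone remodeling". Section 1 describes the study's aim as "to determine whether mandibular anatomy plays a measurable role".
- Section 6.1 is more detailed for the bone measurement itself: "Two calibrated examiners (ICC=0.94) measure MBL; discrepancies >0.1 mm resolved by consensus".
- Section 8 closes with "Secondary analyses are exploratory".

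**The concern.** Intercanine and intermolar widths are named after teeth. The *and/or* in the inclusion criterion could admit a patient with a dentate opposing mandible, but that jaw is not rehabilitated and carries no study implants. Every mandible that is classified therefore lacks the teeth that give the ratio its name, and section 6.2 does not say which points replace them.

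The section also lists two measures but returns one binary class, with no cut-point for either. If each were dichotomised separately, a mandible could be U on one and V on the other, with nothing to settle it.

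Two harms could follow. Random labelling error would pull the U-V difference towards zero, so that a null result might be read as showing that anatomy plays no part. A rule chosen after the bone-loss data had been seen could instead raise the false-positive rate. The label is the only exposure in that secondary objective, and section 6.1 shows that the protocol can be specific about a measurement when it chooses.

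**Working it through.** The protocol states no figure for this comparison, so there is nothing to reproduce. The check is first one of reading, then of scale.

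**Reading.** Set beside section 4, section 6.2 contradicts it only if the ratio must be taken from teeth. The section says the classification is made on CBCT, which images bone. Canine-site and molar-site positions on the ridge are a natural reading, so the ratio can be obtained. What is absent is the name of the landmark. On the second point, section 6.2 joins ratio and angle with *and* and speaks of one categorisation. A composite criterion, or a requirement that both hold, fits that wording as well as two separate labels do. Conflict between labels follows only under the two-label reading.

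**Number of mandibles.** From section 3, 49 − 40 = 9 patients have both arches treated, which leaves 40 − 9 = 31 with one arch. Mandibles number from 9 + 0 = 9 to 9 + 31 = 40. The protocol gives no split.

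**Effect of wrong labels.** Assumptions: true U-V difference 0.2 mm and SD 0.30 mm (section 3 gives these for the sample size, not for U versus V), near-equal groups, error unrelated to bone loss, two-sided 0.05. With a share e mislabelled, the observed difference is 0.2 × (1 − 2e). This gives 0.16, 0.12 and 0.08 mm at e = 10%, 20% and 30%. The standard error is 0.30 × √(1/n₁ + 1/n₂), and power comes from the noncentral t distribution with the SD held at 0.30.

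| Mandibles | SE (mm) | e = 0 | 10% | 20% | 30% |
|---|---|---|---|---|---|
| 9 (4 vs 5) | 0.201 | 14% | 11% | 8% | 6% |
| 25 (12 vs 13) | 0.120 | 36% | 25% | 16% | 10% |
| 40 (20 vs 20) | 0.095 | 54% | 38% | 23% | 13% |

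With no labelling error at all, the 95% interval at 25 mandibles has half-width 2.069 × 0.120 = 0.25 mm, wider than the assumed effect. Even at the maximum of 40 it is 2.024 × 0.0949 = 0.19 mm. A null result would say little however well the mandibles were labelled.

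**Disagreement between measures.** If two bivariate normal measures are each cut at the median, the share that disagree is arccos(ρ)/π. For ρ = 0, 0.5 and 0.8 this is 50%, 33% and 20.5%; for ρ = 0.95 it is 10%. No correlation is given in the protocol. Zero is hard to defend for two measures of the same arch taper, and it produces the largest figures.

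**Choice of rule after the data.** Suppose four rules were open (ratio alone, angle alone, V if both, V if either) and the smallest p-value were reported. In simulation with no true difference, the false-positive rate at 25 mandibles was 15%, 14% and 12% for ρ = 0, 0.5 and 0.8, and about 9% for ρ = 0.95, against a nominal 5%. This needs both the two-label reading and deliberate or unwitting selection. The protocol indicates neither.

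**The case for a change.** The best case for a change is that this concerns how an exposure is measured, which belongs in the protocol and is not something to leave to an analysis plan. The protocol seems to agree: section 6.1 fixes calibration, readers and consensus for bone loss, and section 6.3 names the distal implants and the CAD source for the geometric measures. Section 6.2 alone could not be repeated by another team from its text. A few added lines would cost almost nothing.

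Much of that stands. The landmarks, cut-points and combining rule are not in the protocol, and a reader of the results will need them. But the argument shows that detail is missing, not that a stated rule is wrong. Section 6.2 refers to validated criteria. Such criteria ordinarily come with landmarks and thresholds, and the documents give no ground for saying that these do not. The absence of a citation is not peculiar to this item, since the protocol shows no reference list for any method, OHIP-14 included. Duplicate reading of every scan, masking of readers to bone loss and a sensitivity analysis over alternative rules would be good practice, but they would correct no error in the text. Section 6.1 itself does not state masking.

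**Conclusion.** The observation is accurate, but no change to the plan follows. Section 6.2 leaves a descriptive gap that analysts applying the named criteria to CBCT images of edentulous ridges would fill sensibly. It does not contradict the inclusion criteria, because ridge positions can stand in for absent teeth.

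The primary maxilla-mandible comparison does not use the label. The comparison that does is secondary, declared exploratory, and weak even with perfect labels: 14% power at 9 mandibles, 36% at 25 and 54% at 40, for an assumed 0.2 mm difference with SD 0.30 mm and near-equal groups. The further losses and the inflated false-positive rates rest on error rates, correlations, cuts and a selection process that the protocol does not supply, so they show what could happen and are not evidence that the plan is at fault. The conclusion assumes that the landmarks and rule are settled without reference to the bone-loss results and are described when the U-V comparison is reported.

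### Does analysing mandibular shape only as U versus V, when it is derived from a ratio and an angle, weaken the plan?

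*Protocol*

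**What the plan says.** The shape question is put the same way throughout the protocol.

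- **Section 2 (Secondary Objectives):** "To evaluate whether mandibular morphology (U-shaped vs V-shaped) affects early marginal bone remodeling".
- **Section 3 (Study Groups):** the mandibular group has one sub-analysis, by U or V shape.
- **Section 6.2:** a "CBCT-based classification using validated criteria (intercanine/intermolar ratio and anterior arch angle", ending in a "U-shaped vs V-shaped categorization". The criteria are described as validated; cut-offs are not printed.
- **Section 8:** "Morphology subgroups: One-way ANOVA with Bonferroni". Pearson correlations by arch are also planned, without naming the variables. All secondary analyses are declared exploratory.

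Continuous geometry has its own objective: "To assess associations between arch geometry (inter-implant distance, cantilever length) and MBL". Those two measures come from the CAD designs (section 6.3), not from the CBCT.

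The sample is "49 rehabilitated arches in 40 edentulous patients". The number of mandibles and the U/V split are not given.

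**The concern.** The ratio and the angle are numbers, and the plan reduces them to one of two labels. After that, a mandible just past the boundary counts the same as an extreme one. If bone loss changes gradually with shape, this discards information, and there is little to spare because mandibles are few. The background says the study is meant "to determine whether mandibular anatomy plays a measurable role", which can be read as wider than a two-class contrast. No stated analysis clearly relates bone loss to the numeric shape values: the association objective names only inter-implant distance and cantilever length, and the Pearson line names nothing.

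At stake would be a missed graded relation in a secondary, exploratory question. The primary maxilla-mandible comparison is not touched.

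**Working it through.** **1. Does the analysis match the question?** Objective, sub-analysis, classification and test all use U versus V. The background phrase about mandibular anatomy directly follows a sentence that gives U-shaped and V-shaped arches as the anatomical variation of interest. Nothing is contradicted.

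**2. Is there a stated figure to reproduce?** Not for shape. The only power statement, "Power >85% to detect a 0.2 mm difference in MBL (SD 0.30 mm", belongs to the primary comparison and does not bear on this point. (It does not reproduce at arch level: an even split of the 49 arches gives about 65% two-sided. That is a separate matter.)

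**3. How many mandibles?** If no patient has more than two arches, 49 − 40 = 9 patients have both jaws and 31 have one. Mandibles therefore number between 9 and 9 + 31 = 40. I use 24 as a middle case; this is an assumption.

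**4. Loss if the relation is graded.** For a normal score cut at c with class share p, the class keeps φ(c)²/[p(1−p)] of the information:

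- p = 0.5: 0.3989²/0.25 = 0.637
- p = 0.25: 0.539

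Fisher-z power, two-sided 0.05, n = 24, r = 0.5:

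- Score: atanh(0.5)·√21 − 1.96 = 2.517 − 1.960 = 0.557, power 71%.
- Class: r·√(2/π) = 0.399; atanh(0.399)·√21 − 1.96 = 1.936 − 1.960 = −0.024, power 49%.

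**5. Graded and step relations side by side.** Simulation with a normal score and a cut at its midpoint. r is the correlation of bone loss with the score (graded) or with the class (step). Entries are power, score / class.

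| Mandibles | r | Graded | Step at U/V boundary |
|---|---|---|---|
| 9 | 0.5 | 29% / 18% | 19% / 29% |
| 24 | 0.5 | 73% / 51% | 52% / 75% |
| 40 | 0.5 | 92% / 76% | 77% / 94% |
| 24 | 0.3 | 30% / 20% | 21% / 30% |

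The two columns nearly mirror each other. What the score gains under one pattern it loses under the other.

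**6. How large is r = 0.5?** Take the protocol's SD of 0.30 mm for per-mandible means. A graded r = 0.5 then implies a mean U–V difference of 2 × 0.5 × 0.30 × √(2/π) = 0.24 mm, more than the 0.2 mm used for the primary comparison. At r = 0.3 the difference is 2 × 0.3 × 0.30 × 0.798 = 0.14 mm, and neither analysis has more than about 30% power at 24 mandibles.

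**7. Cost of running both.** Simulation, n = 24, even split:

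- No effect, each test at 0.05: at least one is significant in about 8% of runs.
- Each test at 0.025, r = 0.5: power of the pair is about 66% (graded) or 68% (step). The step figure is below the 75% from the class test alone.

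**The case for a change.** The strongest case for the concern is that the addition is cheap and well aimed. Section 8 itself fixes the shape analysis as a group comparison, so the matter is not wholly left to another document. The other geometric measures are treated as associations, and only shape is reduced to two classes. One exploratory regression, kept beside U versus V and reported as a slope with a confidence interval, would show a gradation that the class cannot. It would also avoid relying on cut-offs that the protocol does not print.

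Part of this stands. The information loss under a graded relation is real and correctly sized, and an exploratory slope reported as an estimate would do no harm.

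The rest does not make it a fault:

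- The protocol gives no reason to expect a graded effect rather than a step.
- The proposed score, an equally weighted mean of the standardised ratio and angle, is not described in the protocol. Its weights are arbitrary, its unit depends on this sample, and its direction would have to be fixed in advance. It would stand beside criteria that the protocol calls validated.
- Section 6.2 describes a classification. It does not say that the ratio and angle are kept as numeric study variables, so it is an inference that no new data would be needed.
- The slope would be imprecise. With a residual SD of 0.30 mm, the 95% half-width is 2.074 × 0.30/√23 = 0.13 mm per SD of score at 24 mandibles, and 2.365 × 0.30/√8 = 0.25 mm at 9. At r = 0.5 the residual SD falls to 0.30 × √0.75 = 0.26 mm and the half-width at 24 to 0.11 mm, against a slope of 0.5 × 0.30 = 0.15 mm.

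**Conclusion.** The concern does not hold. The protocol asks whether U-shaped and V-shaped mandibles differ, classifies them that way, and tests that difference. Using only the class misstates nothing and contradicts nothing.

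A continuous analysis is not a better method on the protocol's own terms. At 24 mandibles and r = 0.5 it gains about 22 points of power if the effect is graded (73% against 51%) and loses about 23 if it is a step (52% against 75%). Testing both ways at 0.05 carries a false-positive chance of about 8%. Whether to add it is a modelling preference about an exploratory secondary question. A separate SAP, if one exists, may already contain it.

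The power figures assume a normal shape score, an even U/V split, the stated mandible counts and correlations, and two-sided testing. None of these is given in the protocol. The conclusion does not depend on their exact values, because the reversal between graded and step relations appears at 9, 24 and 40 mandibles and at both correlations tried with 24.
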